## Figure 2: Treatment Satisfaction instrument

### **NUMERICAL RATING SCALE (NRS) FOR TREATMENT SATISFACTION**

Consider all the good and bad things about this treatment. Overall, how satisfied are you with the treatment?  
(circle one)

-3	Very dissatisfied
-2	Moderately dissatisfied
-1	Mildly dissatisfied
1	Mildly satisfied
2	Moderately satisfied
3	Very satisfied

Source: Salame N, Perez-Chada LM, Singh S, Garg KA, Gottlieb AB, Latella J, Merola, JF, Armstrong AW. International Dermatology Outcome Measures (IDEOM) Annual Meeting. Washington, DC. May 2019.

## Appendix 1: Evaluation Schedule

Visit	Wk 0 Screening/ Baseline	Wk 2	Wk 8	Wk 12	Wk 16	Wk 24/ Early Termina- tion
Inclusion/Exclusion criteria	X					
Informed consent	X					
Review medical history, including previous and concomitant therapies	X					
Adverse events		X	X	X	X	X
Review con meds	X	X	X	X	X	X
Physical examination	X					X**
Urine pregnancy test*	X					
ppPGA	X	X	X	X	X	X
DLQI		X	X	X	X	X
NRS for treatment satisfaction		X	X	X	X	X
Photography	X	X	X	X	X	X
Dispense drug	X	X	X			X
Collect Drug		X	X		X	X

\*Urine pregnancy test is required for pre-menopausal female subjects only.

\*\*Physical examination is only required for early termination

ppPGA: Palmoplantar Physician Global Assessment is based on the Investigators Global Assessment (IGA) modified version 2011, specifically applied to the palms and soles and consisting of a 5-point scale: 0 (clear), 1 (almost clear/minimal), 2 (mild), 3 (moderate), 4 (marked/moderate-to-severe), 5 (severe).

DLQI: Dermatology Quality of Life Index is a 10 question dermatology-specific quality of life questionnaire.

NRS for treatment satisfaction: Numerical Rating Scale consisting of 1 question: "Consider all the good and bad things about this treatment. Overall, how satisfied are you with the treatment?" Answer options: -3 (very dissatisfied), -2 (moderately satisfied), -1 (mildly satisfied), 1 (mildly satisfied), 2 (moderately satisfied), 3 (very satisfied)

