Statistical Analysis	Assuming the 40% of patients achieve ppPGA of 0 or 1 (similar to that seen with secukinumab) at week 24, this study requires 22 patients with a statistical power of 0.8 and 5% type one error
Budget Estimate	
\$120,845
 
88 tubes of Duobrii® (4 tubes of Duobrii® for each subject) supplied by Ortho Dermatologics.
 
The medication will be dispensed to the subject at week 0,2,8,16 and returned by the

	
subject at week 2,8,16,24.
 
Subjects will be compensated \$40 per study visit for their time and effort in participating in this study.

--	--

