## **Study Treatments**

Upon enrollment in the study, each subject will be given a supply of HP/TAZ at visits 0,2,8,16 to be used over the 24 weeks. Each subject will be instructed to apply a thin layer HP/TAZ to affected areas of palms and/or soles once a day for the duration of the study (i.e. daily treatment for 24 weeks).

All study treatments will be completed by the subject and will occur in the home setting. Subjects will be encouraged to record and report any missed treatments. Patients will be allowed to use OTC moisturizers, but should not apply them the days of their visits.

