## **Study Procedures & Guidelines**

The study is designed to include six study visits over 24 weeks. The procedures performed at each study visit are detailed below. All procedures will be performed at the single study site. They will also be instructed to store the investigational drug at 20 to 25 °C (68 to 77 °F), and to not freeze the drug.

A table detailing the study procedures is found in Appendix 1. All study visits and procedures will be documented in source documents created specifically for this study that will be completed in accordance with Good Clinical Practice (GP) documentation principles (i.e. attributable, legible, contemporaneous, original, accurate, enduring, available and accessible, complete, consistent, credible, and corroborated).

- I. Week 0 (Screening/Baseline)
  - A. Review Inclusion/Exclusion criteria
  - B. Obtain written informed consent
  - C. Review medical history and previous failed therapies

- D. Review concomitant medications
- E. Perform physical examination
- F. Obtain urine pregnancy test (for pre-menopausal female subjects only)
- G. Evaluate ppPGA
- H. Obtain photographs of affected areas
- I. Dispense study drug

II. Week 2

- A. Review adverse events
- B. Review concomitant medications
- C. Evaluate ppPGA
- D. Administer DQLI
- E. Administer NRS for treatment satisfaction
- F. Obtain photographs of affected areas
- G. Dispense study drug
- H. Collect study drug

III. Week 8

- A. Review adverse events
- B. Review concomitant medications
- C. Evaluate ppPGA
- D. Administer DQLI
- E. Administer NRS for treatment satisfaction
- F. Obtain photographs of affected areas
- G. Dispense study drug
- H. Collect study drug

IV. Week 12

- A. Review adverse events
- B. Review concomitant medications
- C. Evaluate ppPGA
- D. Administer DQLI
- E. Administer NRS for treatment satisfaction
- F. Obtain photographs of affected areas

V. Week 16

- A. Review adverse events
- B. Review concomitant medications
- C. Evaluate ppPGA
- D. Administer DQLI

- E. Administer NRS for treatment satisfaction
- F. Obtain photographs of affected areas
- G. Dispense study drug
- H. Collect study drug

VI. Week 24

- A. Review adverse events
- B. Review concomitant medications
- C. Evaluate ppPGA
- D. Administer DQLI
- E. Administer NRS for treatment satisfaction
- F. Obtain photographs of affected areas
- G. Collect study drug

VII. Early Termination

- A. Review adverse events
- B. Review concomitant medications

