- C. Evaluate ppPGA
- D. Administer DQLI
- E. Administer NRS for treatment satisfaction
- F. Obtain photographs of affected areas
- G. Collect study drug
- H. Physical examination

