## Protocol Violations

Subjects may withdraw from the trial at any time at their request (verbal or written), or they may be withdrawn at any time at the discretion of the Sponsor, PI, or designee for safety, behavioral, or administrative reasons. Subjects may be withdrawn from this study without their consent if the research study is being stopped; or if the instructions of the study team have not been followed.

Any enrolled subject who will not be completing the duration of the study will be asked to complete an Early Termination study visit, consisting of the procedures indicated below. In addition, the reason for Early Termination will be recorded in the source documents.

- 1) Review medical history
- 2) Review concomitant medications
- 3) Perform physical examination
- 4) Obtain urine pregnancy test (for pre-menopausal female subjects only)
- 5) Evaluate ppPGA
- 6) Administer DQLI

- 7) Administer NRS for treatment satisfaction
- 8) Obtain photographs of affected areas

If a subject is unable or unwilling to complete an Early Termination visit, this will be documented in the source documents.

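### Appendix 1, as extracted, dispenses drug at Week 24/Early Termination and not at Week 16, while the text dispenses at Week 16 and only collects at exit

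*Combined protocol and SAP*

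**What the plan says.** **Dispensing and return in the text.** The Budget Estimate row of the Protocol Synopsis states: "The medication will be dispensed to the subject at week 0,2,8,16 and returned by the" subject at Weeks 2, 8, 16 and 24. Study Treatments agrees: "each subject will be given a supply of HP/TAZ at visits 0,2,8,16 to be used over the 24 weeks". In Study Procedures & Guidelines, the Week 16 list has both a dispensing and a collection item. The Week 24 and Early Termination lists each have "G. Collect study drug" and no dispensing item.

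**Dispensing and return in the table.** Appendix 1 has six visit columns: Weeks 0, 2, 8, 12, 16 and 24/Early Termination. The dispensing row, "Dispense drug X X X X", has its marks under Weeks 0, 2, 8 and 24/Early Termination. The collection row, "Collect Drug X X X X", has its marks under Weeks 2, 8, 16 and 24/Early Termination.

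**Standing of the two sources.** Study Procedures & Guidelines introduces its visit lists with "The procedures performed at each study visit are detailed below" and then adds "A table detailing the study procedures is found in Appendix 1". It does not say which governs if they differ.

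**A second Early Termination list.** Protocol Violations describes an "Early Termination study visit, consisting of the procedures indicated below" and gives eight items. None concerns study drug.

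**The concern.** A visit-by-visit table is a natural basis for source documents and dispensing logs, and this one does not match the text. Read as it stands, Appendix 1 takes drug back at Week 16, issues none, and issues drug again at the exit visit.

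Two things would follow if site staff worked from the table. First, subjects would have no supply between Week 16 and Week 24. The primary ppPGA assessment would then not follow the 24 weeks of daily treatment that Criteria for Evaluation and Study Treatments require. Secondly, drug would leave the site at the final or early-termination visit. Study Timeline makes Week 24 the last visit, so no later visit is scheduled at which to collect that drug or review adverse events.

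The Early Termination visit is also described in three places that do not agree on drug handling.

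**Working it through.** **Inputs.** Dispensing and return weeks come from the Synopsis, Study Treatments, Study Procedures & Guidelines and Appendix 1. Once-daily treatment for 24 weeks comes from Study Treatments. The supply of 88 tubes, 4 per subject, comes from the Synopsis.

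**Step 1: the plan's own supply figure.** 22 subjects × 4 tubes = 88 tubes, which reproduces the stated total. Text and table each have four dispensing occasions, so this figure fits both and cannot show which is intended.

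**Step 2: the schedules side by side.**

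| Source | Dispense | Collect |
|---|---|---|
| Synopsis | 0, 2, 8, 16 | 2, 8, 16, 24 |
| Study Treatments | 0, 2, 8, 16 | not stated |
| Visit lists, scheduled visits | 0, 2, 8, 16 | 2, 8, 16, 24 |
| Appendix 1, as extracted | 0, 2, 8, 24/Early Termination | 2, 8, 16, 24/Early Termination |

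The collection rows agree. The only difference is the fourth dispensing mark.

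**Step 3: weeks of supply.** Each supply lasts from its dispensing to the next collection, on the assumption that collected drug is not handed back.

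- Text: (2 − 0) + (8 − 2) + (16 − 8) + (24 − 16) = 2 + 6 + 8 + 8 = 24 weeks. Uncovered: 0.
- Table: 2 + 6 + 8 = 16 weeks. Uncovered: 24 − 16 = 8 weeks, and 8/24 = 33%.
- In once-daily applications per subject: 8 × 7 = 56 uncovered of 24 × 7 = 168.

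**Step 4: is the position of the mark credible?** The dispensing row has seven cells (a label and six visits), as the header does. That alone proves little, because a mark moved by one column would leave the count unchanged. The neighbouring rows say more:

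- The other 12 of the 13 rows in Appendix 1 have their marks where the visit lists require.
- The collection row, directly below, also has a blank at Week 12 and still lines up with the text.
- The physical-examination row has a run of blanks and then a mark in the last column. Its footnote, restricting that mark to early termination, confirms the position. The dispensing mark in the same column has no such footnote.

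**Step 5: Early Termination.**

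| Source | Drug handling |
|---|---|
| Study Procedures & Guidelines, list VII | collect |
| Protocol Violations, eight-item list | neither |
| Appendix 1, as extracted | collect and dispense |

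The first two are running lists, so their disagreement does not depend on how the table was read. The third depends on the same mark as Steps 2 to 4.

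**The case against.** The strongest reply is that the main discrepancy is one mark in a table read from PDF by a program. Moving it one cell to the left makes the row agree exactly with the text, which is what an extraction slip would look like. A typing error in the original would look the same. This cannot be settled without the page, and it stands as a limit on the finding. The neighbouring rows favour a real discrepancy but do not prove one.

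It can also be said that the text is complete and consistent on its own. To lose 8 weeks of supply, staff at a single site would have to follow the table against the Synopsis, Study Treatments and the visit lists. That is fair: the figures of 33% and 56 of 168 describe a conditional risk, not an expected loss.

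Finally, the count of three Early Termination versions falls to two if the mark belongs at Week 16, and Protocol Violations differs by silence, not by forbidding collection. The first part is right. On the second, that section says what the visit consists of, so leaving collection out is a difference in instruction. The two lists therefore need reconciling whatever the page shows.

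**Conclusion.** The concern holds. As extracted, Appendix 1 and the text give different dispensing schedules, and the protocol refers staff to both without an order of precedence. If the table is followed, 8 of 24 weeks of supply (33%; 56 of 168 applications per subject) are missing immediately before the primary assessment, and drug is issued at exit. If the text is followed, nothing is lost.

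This rests on the extracted position of one mark, on collected drug not being returned to the subject, and on the table being used in practice. Confidence in the Appendix 1 point is therefore medium. The conflict between the two Early Termination lists depends on none of these. The point should be fixed; it does not affect the sample size. No view is taken on which schedule is right.

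**What to change.** 1. Check the dispensing row on the original page of Appendix 1.
2. Reconcile the Synopsis, Study Treatments, Study Procedures & Guidelines, Protocol Violations and Appendix 1 so that they give one dispensing and collection schedule, including at Early Termination.
3. Check the source-document templates and dispensing logs against the reconciled schedule.

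The cost is an administrative amendment to whichever sections change, plus the check of templates and logs. The number of subjects and the visits stay as they are.
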